9.2 Appendix B – Application of Comprifore system

Comprifore compression system application instructions:

The application of JOBST® Comprifore #1 to #4:

Ensure the ankle is dorsiflexed at 90 degrees when applying each bandage (toes to the nose). Place Comprifore #1 at the base of the toes, wrap the foot twice to anchor the bandage firmly.

Cover the heel and proceed up the leg using the spiral wrapping technique at 50% overlap with low tension. Finish just below the knee. Excess bandage can be removed and used as additional padding if required.

Apply Comprifore # 2 bandage with two anchor turns at the base of the toes, cover the heel and proceed with 50% overlap using the spiral technique and just enough tension to fully extend the bandage. Cut off and discard any excess bandage.

Apply Comprifore # 3 light compression with two anchor turns at the base of the toes, cover the heel and proceed with 50% stretch using the Figure of Eight technique to generate the correct pressure and improve pressure distribution. Cut off any excess bandage.

Apply Comprifore # 4 with 2 anchor turns at the base of the toes, cover the heel and proceed with a spiral technique at 50% overlap and 50% extension to the base of the knee. Cut off any excess bandage.

Gently smooth and squeeze the outer layer to smooth and settle the layers and secure the system in place.

9.3 Appendix C – Ankle brachial index measurement

Technique:

1. Check that all needed equipment is available and functioning properly.
2. Explain to the subject what you are about to do and inform them there may be slight discomfort as the cuff inflates.
3. Place the subject in a supine position. Ensure the arms and legs at the same level as the heart.
4. Hold the subject in this position for 10 minutes before measurement.
5. Apply appropriate size blood pressure cuff to the arms and ankles and obtain systolic pressure.
Note: cuff size should be at least 20% greater than the limb diameter
6. Obtain systolic pressure on the leg with the study ulcer from the tibialis posterior and the dorsalis pedis arteries.
7. Calculate the ABI using the higher systolic pressure of the arms and ankle using the following formula:

$$\text{ABI} = \text{higher brachial pressure} / \text{higher ankle pressure}$$

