Venous leg ulcers, the problem: Leg ulcers are very common and affect about 1-2% of the American population [2]. Venous leg ulcers (VLU) are wounds that occur in the gaiter area in the setting of chronic venous insufficiency (CVI). VLU account for about 70% of the all chronic leg ulcers and about 20% of all leg ulcers are likely a result on mixed arterial and venous disease. VLU significantly impacts patients' quality of life [4] and people with VLU are often chronically ill with significantly more comorbid conditions compared to controls [5]. VLU represent an increasingly devastating economical burden. For example, the estimated cost of treating single non healing VLU in 1987 was \$10,000 and by 2014 has ballooned to \$34,000 [6]. This is also reflected by the 5-fold increase in total cost of VLU treatment from estimated \$3 billion to \$15 billion over a similar period. The prevalence of VLU is difficult to assess yet recent estimates suggest a significant rise from 0.3% 20 years ago to more recent estimates of 0.6% in adults under 65 years of age and 2.2% in adults over 65 . Considering the aging of the population a concerning picture emerges: more ulcers occurring in sicker patients which are ever more expensive to treat. Standard care for VLU centers around edema reduction via compression and/or leg elevation, meticulous local wound care, control of infection and pain and prevention of recurrence [7]. Advanced therapies include highly absorbent dressing, matrix based

devices with and without cells and negative pressure wound therapy among others. However even with best therapies available up to 50% of VLU fail to heal [8].

Infections play a significant role in the chronicity of VLU. The high wound bacterial burden ($>10^5$ organisms per gram of tissue), even without the classic signs of infection, is also detrimental to healing [9, 10].

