4.2 Criteria for inclusion

Criteria for inclusion in the study:

1. Adults, 18 years old and older (i.e. age \geq 18 years).
2. Venous leg ulcer (VLU) is present on the leg. VLU shall be full thickness but without exposure of deeper tissues (muscle bone or tendon).
3. If more than one ulcer is present, the largest ulcer meeting criteria shall be designated the study ulcer.
4. If more than one ulcer on the study ulcer limb, study ulcer shall be at least one centimeter from other ulcers.
5. Confirmed venous insufficiency, as documented up to 30 days prior to enrollment (Baseline Day 0), by either: a) Duplex ultrasonography, or b) Principal Investigator (PI) clinical assessment to include clinical signs and symptoms of venous ulcerations (e.g., hyperpigmentation of surrounding skin, varicosities, and/or lipodermatosclerosis).
6. Ankle-Brachial Pressure Index (ABI) exam with value of ≥ 0.80 in the affected limb
7. VLU has been treated with silver based therapy for at least 2 weeks within the previous 6 months.
8. VLU present for at least one month prior to screening visit 1.
9. VLU at least 1 cm in size but not larger than 100 cm².
10. After debridement, study ulcer demonstrates a clean wound bed.
11. If subject is a female of childbearing potential, subject must use at least one method of contraception acceptable by PI such as birth control pills, IUD, condoms, or sexual abstinence. At visit 1 urine pregnancy test must be negative.
12. Subject is able to comprehend all study related procedures and adhere to study schedule.
13. Subject is able to provide written informed consent.

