4.3 Criteria for exclusion

Criteria for exclusion from the study:

1. Based on investigator medical judgment, ulcer is caused by any etiology exclusive of venous insufficiency.
2. Study Ulcer surface area (post-debridement) has increased or decreased by more than 30% in the period between screening visit 1 and treatment visit 1.

3. Study Ulcer exhibits clinical signs and symptoms of infection in the period between screening visit 1 and treatment visit 1 requiring oral antibacterial therapy.
4. Subject has known allergy to any of the materials used in the study.
5. Subject is unable to tolerate multi-layer compression therapy.
6. Based on investigator medical judgment, the Study Ulcer is suspicious for cancer (e.g. basal cell carcinoma or squamous cell carcinoma).
7. In the month prior to screening visit 1 subject was treated with systemic immunosuppressive medications for more than 2 weeks (e.g. chemotherapy, corticosteroids), and/or it is anticipated subject will require such medications during study period.
8. In the month prior to screening visit 1 subject was enrolled in any other research protocol for treatment of Study Ulcer.
9. The Subject has been diagnosed with malignant disease not in remission over the 5 years immediately preceding screening visit 1. (Except: cervical carcinoma in situ, cutaneous squamous cell carcinoma, cutaneous basal cell carcinoma that have been treated and have no evidence of recurrence or metastases).
10. Study ulcer area has been treated with radiation therapy at any time.
11. In the opinion of PI the subject has a medical condition such as autoimmune, renal, hepatic or hematologic disease that makes the subject an inappropriate candidate for participation in study.
12. In the month preceding screening visit 1 Study Ulcer has been treated with advanced tissue engineered devices matrix based devices (e.g., Apligraf™, Dermagraft™, Oasis™).
13. Subject is diagnosed with New York Heart Association Class III and IV congestive heart.
14. Failure: Class III: Symptoms with moderate exertion or, Class IV: Symptoms at rest.
15. Subject is diagnosed with diabetes mellitus that is poorly controlled and shall be defined as hemoglobin A1C >10%.
16. Study Ulcer is completely or more than 50% of the Study Ulcer is located on the foot (i.e. below the malleolus).

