5.18 Compression

Four-layer compression will be standard care for all subjects. The Comprifore® system will be used as described in Appendix B.

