5.22 Ankle- brachial – index (ABI)

ABI should be calculated for all subjects during visit S1. The protocol for measuring and calculating ABI is detailed in appendix C. The result of the test should be documented in the CRF.

6. Study conduct

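### Appendix C inverts the ABI (brachial over ankle), so the ≥ 0.80 entry criterion passes every limb with low ankle pressure and fails only limbs whose ankle pressure is more than 25% above brachial

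*Combined protocol and SAP*

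**What the plan says.** Three places fix how the ABI is obtained and used.

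- Section 4.2, inclusion criterion 6, requires an "Ankle-Brachial Pressure Index (ABI) exam with value of ≥ 0.80 in the affected limb". This is a floor; no upper limit is given.
- Section 5.22 states that "ABI should be calculated for all subjects during visit S1" and that "The protocol for measuring and calculating ABI is detailed in appendix C". It asks for the test result to be entered in the CRF and does not mention the component pressures.
- Section 9.3 (Appendix C) gives the instruction "Calculate the ABI using the higher systolic pressure of the arms and ankle using the following formula", followed by a formula with "higher brachial pressure} / \text{higher ankle pressure" on the right-hand side.

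No other ABI formula appears in the documents. Two further statements give the context. Section 5.18 says "Four-layer compression will be standard care for all subjects", and the Background (section 2) says that "about 20% of all leg ulcers are likely a result on mixed arterial and venous disease". Table 1 schedules the ABI at S1 only, and compression begins at that same visit.

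**The concern.** An ankle-brachial index is, by its name, ankle pressure relative to brachial pressure. Appendix C has it the other way round. Combined with a lower limit, the inversion reverses the screen: the lower the ankle pressure, the larger the computed index and the more easily the limb passes.

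The protocol does not state the purpose of criterion 6. A floor on this index, in a trial that applies four-layer compression to everyone and whose Background separates mixed arterial-venous ulcers from venous ones, is most naturally read as a screen against arterial disease. Two things are then at stake. The first is safety: the only numeric arterial check before compression would not work. The second is the study population: ulcers with an arterial component could enter a trial meant for venous leg ulcers and add variation to the healing outcomes, with only 15 completers planned per arm (section 4.1).

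**Working it through.** The 0.80 limit is a chosen cut-off, so there is no derived figure to reproduce. The check is algebra on the written rule.

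**Inputs.** Let A be the higher ankle systolic pressure and B the higher brachial systolic pressure (section 9.3). The threshold is ≥ 0.80 (section 4.2, criterion 6). The pressures below are illustrative, since the documents give none. Only the ratio matters, so the choice of B does not affect the result.

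**Rule as written.** B/A ≥ 0.80 ⇔ A/B ≤ 1/0.80 = 1.25. There is no lower bound on A/B, so no low ankle pressure can fail.

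**Rule with ankle in the numerator.** A/B ≥ 0.80 ⇔ A ≥ 0.80 × B. At B = 140 mmHg this is A ≥ 112 mmHg.

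**Both rules at B = 140 mmHg:**

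| A (mmHg) | A/B | A/B ≥ 0.80? | B/A (Appendix C) | B/A ≥ 0.80? |
|---|---|---|---|---|
| 56 | 0.40 | fail | 2.50 | pass |
| 70 | 0.50 | fail | 2.00 | pass |
| 84 | 0.60 | fail | 1.67 | pass |
| 98 | 0.70 | fail | 1.43 | pass |
| 110.6 | 0.79 | fail | 1.27 | pass |
| 112 | 0.80 | pass | 1.25 | pass |
| 140 | 1.00 | pass | 1.00 | pass |
| 168 | 1.20 | pass | 0.83 | pass |
| 175 | 1.25 | pass | 0.80 | pass (at limit) |
| 176.4 | 1.26 | pass | 0.79 | fail |
| 182 | 1.30 | pass | 0.77 | fail |
| 196 | 1.40 | pass | 0.71 | fail |

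A different brachial pressure gives the same pattern. With B = 120 and A = 155, A/B = 155/120 = 1.29 (pass), while B/A = 120/155 = 0.77 (fail).

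**Where the rules differ.** For A/B from 0.80 to 1.25 the decisions agree. Below 0.80 the written rule admits every limb that criterion 6 would otherwise exclude. Above 1.25 it excludes limbs that criterion 6 would otherwise admit.

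**Consequence for values already recorded.** If a recorded value v lies between 0.80 and 1.25, its reciprocal lies in the same interval (1/0.80 = 1.25 and 1/1.25 = 0.80). Eligibility on criterion 6 is then the same whichever way v was computed. Only values above 1.25 or below 0.80 depend on the orientation used.

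**Other checks in the plan.** Exclusion criterion 1 reads "Based on investigator medical judgment, ulcer is caused by any etiology exclusive of venous insufficiency". It rests on judgment, and taken literally it does not clearly cover an ulcer of mixed cause. The focused examination (section 5.13) includes leg pulses, skin temperature and capillary refill, with no pass or fail rule. Exclusion criterion 5 concerns tolerance of multi-layer compression. The Doppler study in Table 1 is venous. None of these has a numeric arterial limit or corrects the formula.

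**The case against.** The inversion itself is hard to dispute. The case on the other side concerns its reach.

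- *Experienced staff probably compute the ratio the usual way round.* That may be so, and the documents cannot settle it. What can be supported is that the written rule permits wrong admissions, not that any have occurred. A protocol should still not depend on staff departing from its own formula, and mixed practice would leave the recorded values uninterpretable.
- *Limbs with good ankle pressure are mostly not rejected.* This stands. Only those with ankle pressure more than 25% above brachial are turned away.
- *Clinical judgment, the pulse examination and the compression-tolerance exclusion offer some protection.* This also stands: they may catch some arterial disease. They do not replace a numeric criterion.
- *The 20% figure refers to all leg ulcers, not to patients screened here.* Correct. It shows that mixed disease is a realistic possibility, but it does not estimate how many subjects would be wrongly admitted.
- *The safety argument goes beyond the text.* In part. The documents do not say that low ankle pressure makes compression unsafe, nor why criterion 6 exists. The contradiction between the formula, the index's name and the direction of the floor needs no outside source.
- *The effect on outcomes is not quantified, and healing is secondary.* This stands. No effect on bacterial load, the primary outcome, has been shown.

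**Conclusion.** The concern holds. Under Appendix C as written, criterion 6 is equivalent to ankle/brachial ≤ 1.25: it passes every limb below 0.80 and fails only those above 1.25. The result is exact and does not depend on the pressures chosen for illustration. It assumes only that staff follow the printed formula, which section 5.22 directs them to do. A typesetting or reading fault is conceivable but unlikely for two labelled terms, and the sentence introducing the formula also names the arms before the ankle.

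The number of subjects affected cannot be estimated from the documents. The sample size and the primary analysis are untouched. Because the error reverses the only numeric arterial screen in a trial with compression for all, it needs correcting before the criterion is relied on.

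**What to change.** Reconcile Appendix C with inclusion criterion 6 by exchanging numerator and denominator, so that the index is the higher ankle pressure divided by the higher brachial pressure. This is the only orientation consistent with the index's name and with the use of a floor. It corrects a calculation; the sponsor's 0.80 threshold is not at issue here and is left unchanged.

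Two accompanying steps are needed:

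1. Record both component pressures in the CRF alongside the ratio, and correct any ABI formula printed on the form. The CRF is not among the documents, so whether it carries one is unknown.
2. For anyone already screened, establish which orientation was used and recompute from the pressures where these were kept. Where only the ratio survives and it was computed as Appendix C states, its reciprocal is the index. Start with enrolled subjects whose recorded value exceeds 1.25 and screen failures below 0.80, since eligibility on this criterion is unaffected for values between those limits.

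The cost is a one-line amendment, a small CRF change and a short check of existing records. No procedures, visits or patients are added.

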9.4 Appendix D – itch assessments

Itch Numeric Rating Scale:[35]

Please circle the number that best describes the level of itch around your wound in the last 24 hours:

0	1	2	3	4	5	6	7	8	9	10
---	---	---	---	---	---	---	---	---	---	----

No itch

Worst
imaginable itch

Please circle the number that best describes the level of itch over your whole body in the last 24 hours:

0	1	2	3	4	5	6	7	8	9	10
---	---	---	---	---	---	---	---	---	---	----

No itch

Worst
imaginable itch

9.5 Appendix E – Insight wound imaging system

inSight™ 3D Measurement Guide

LL-5005 Rev. B 07/27/2016

Learn how to obtain accurate and consistent 3D measurements

① Start Measurement

Click "Measure Wound" in Wound Summary page

③ Define Wound Border

- Roughly sketch outside the wound
- Roughly sketch inside the wound
- Border is automatically defined
- Adjust border as necessary or use manual tracing

e. Click "Measure"

! Best Practices

- Hold the sensor perpendicular to the wound bed
- Capture image from the optimal distance (follow the crosshair guide)
- Ensure adequate ambient lighting
- Do not use sensor during or immediately after charging the sensor (charging iPad is okay)

! Know the Limitations

- Tunneling and Undermining: we can't measure what we can't see
- The tip of a structure (e.g. Toes):

3. Circumferential wounds: coming soon with inSight™ 2.0

Need Additional Help?

Log on to portal.ekareinc.com to access the Help Center in the main menu.

eKare, Inc. [name]
[name]
For more information, visit www.ekareinc.com
[contact] [name]

©2016 eKare Inc. All Rights reserved.

iPad is a trademark of Apple Inc., registered in the U.S. and other countries. Structure is a trademark of Occipital, Inc., registered in the U.S.

inSight™ Starter Guide

LL-5005 Rev. B 07/27/2016

Welcome to the new era of wound measurement!

What's In the Box?

- iPad tablet
- Structure Sensor
- Battery Charger x2
- Lightning Cable
- Data Cable
- Manuals

! inSight™ comes pre-calibrated

Connect your Sensor to iPad as shown.
Note location of charging port (in red).

② Create a Patient

! Need to obtain patient consent to store images.

③ Create a Wound

New Patient
AGE/SEX
DOB
MRN

Access eKare app on Home screen:
WOUND CARE, SIMPLIFIED
www.ekareinc.com

- Ensure good lighting condition
- Ensure stable internet connection

④ Start 3D Measurement

That's it! You got the 3D measurement.

Need Additional Help?

Log on to portal.ekareinc.com to access the Help Center in the main menu.

Alternatively, go to Menu -> [Help] -> [Help Center] in the eKare mobile app.

iPad is a trademark of Apple Inc., registered in the U.S. and other countries. Structure is a trademark of Occipital, Inc., registered in the U.S.

eKare, Inc. [name]
[name]
For more information, visit www.ekareinc.com
[contact] [name]
©2016 eKare Inc. All Rights reserved.

9.6 Appendix F – Acticoat® application instructions*

Application:

Follow standard protocol to cleanse wound; do not use oil-based cleansing agents.

For heavily exudative wounds:

Remove the ACTICOAT dressing from the package and cut to size.

Apply the dry ACTICOAT dressing to the wound, either side down, as the exudate will be sufficient to activate the dressing.

Cover the ACTICOAT dressing with an absorbent secondary dressing.

Complete the dressing with appropriate gauze wrappings if necessary.

For all other wounds:

Remove the ACTICOAT dressing from package and cut to shape.

Moisten the dressing with sterile water (do not use saline).

Allow the dressing to drain on an absorbent surface in a sterile field for at least 2 minutes.

Apply the ACTICOAT dressing to the wound surface, either side down.

Cover the dressing with a moist absorbent secondary dressing which may be prepared by saturating gauze with sterile water and wringing out the excess water.

Complete the dressing with appropriate gauze wrappings if necessary.

If the dressing dries and adheres to the wound, moisten or soak the dressing prior to removal.

Avoid forceful removal of the dressing and disruption of the healing wound.

* Source: <http://www.smith-nephew.com/professional/products/advanced-wound-management/acticoat/acticoat/>

9.7 Appendix G

Wound-QoL questionnaire on quality of life with chronic wounds

With the following questions, we aim to find out how your chronic wound(s) affect(s) your quality of life.

Please tick one box per line!

In the last seven days...

		not at all	a little	moderately	quite a lot	very much
1	...my wound hurt					
2	...my wound had a bad smell					
3	...there was a disturbing discharge from the wound					
4	...the wound has affected my sleep					
5	...the treatment of the wound has been a burden to me					
6	...the wound has made me unhappy					
7	...I have felt frustrated because the wound is taking so long to heal					
8	...I have worried about my wound					
9	...I have been afraid of the wound getting worse or of new wounds appearing					
10	...I have been afraid of knocking the wound					
11	...I have had trouble moving about because of the wound					
12	...climbing stairs has been difficult because of the wound					
13	...I have had trouble with day-to-day activities because of the wound					
14	...the wound has limited my leisure activities					
15	...the wound has forced me to limit my activities with others					
16	...I have felt dependent on help from others because of the wound					
17	...the wound has been a financial burden to me					

"Wound-QoL" questionnaire on Health-related Quality of Life in Chronic Wounds • Augustin et al. 2014;
Blome et al. 2014

9.8 Appendix H - EQ-5D-5L instrument

Under each heading, please tick the ONE box that best describes your health TODAY.

MOBILITY

I have no problems in walking about	
I have slight problems in walking about	
I have moderate problems in walking about	
I have severe problems in walking about	
I am unable to walk about	

SELF-CARE

I have no problems washing or dressing myself	
I have slight problems washing or dressing myself	
I have moderate problems washing or dressing myself	
I have severe problems washing or dressing myself	
I am unable to wash or dress myself	

USUAL ACTIVITIES (e.g. work, study, housework, family or leisure activities)

I have no problems doing my usual activities	
I have slight problems doing my usual activities	
I have moderate problems doing my usual activities	
I have severe problems doing my usual activities	
I am unable to do my usual activities	

PAIN / DISCOMFORT

[figure not shown]
I have no pain or discomfort	
I have slight pain or discomfort	
I have moderate pain or discomfort	
I have severe pain or discomfort	
I have extreme pain or discomfort	

ANXIETY / DEPRESSION

I am not anxious or depressed	
I am slightly anxious or depressed	
I am moderately anxious or depressed	
I am severely anxious or depressed	
I am extremely anxious or depressed	

- We would like to know how good or bad your health is TODAY.
- This scale is numbered from 0 to 100.
- 100 means the best health you can imagine.
0 means the worst health you can imagine.
- Mark an X on the scale to indicate how your health is TODAY.
- Now, please write the number you marked on the scale in the box below.

YOUR HEALTH TODAY =

